- Perform 12 lead ECG after each injection.
- Collect any new adverse events after each injection.
- Complete VAS score immediately after EP and at 5 and 10 minutes post each injection.
- Download EP Data.
- Before the participant is discharged, we will wait until his or her vital signs are normal or have returned to their baseline before the injection.
- Normal vital sign ranges for the average healthy adult while resting are:
 - Blood pressure: systolic >90 and <140 mmHg, diastolic >60 and <100mmHg
 - Breathing: >9 and <20 breaths per minute

- Pulse: 60 to 100 beats per minute
- Temperature: Afebrile
- If the vitals do not return to baseline in 4 hours, the subjects will be maintained for observation in the hospital for continuous monitoring. This hospitalization will not be considered a SAE but a protocol procedure unless the event progresses and places the subject at risk.
- Participants will be reminded of the safety risk information included in the informed consent.

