10 EVALUATION OF SAFETY AND MANAGEMENT OF TOXICITY

10.1 Safety Parameters

The safety of AZD5396 and AZD8076 with Hylenex® Recombinant and CELLECTRA™ 2000 will be measured and graded in accordance with the “Toxicity Grading Scale for Healthy Adult and Adolescent Volunteers Enrolled in Preventive Vaccine Clinical Trials,” issued September 2007 ([Appendix B: Toxicity Grading Scale](#)).

10.1.1 **Definition of Adverse Events (AE)**

An adverse event (AE) is any untoward medical occurrence associated with the use of an intervention in humans, whether or not considered intervention related. Intercurrent illnesses or injuries should be regarded as adverse events.

A pre-existing condition should be recorded as an adverse event if the frequency, intensity, or the character of the condition changes.

Abnormal Laboratory Values

A clinical laboratory abnormality should be documented as an adverse event if any of the following conditions is met:

- The laboratory abnormality is not otherwise refuted by a repeat test to confirm the abnormality.
- The abnormality suggests a disease and/or organ toxicity.
- The abnormality is of a degree that requires active management.

10.1.2 **Definition of Serious Adverse Events (SAE)**

Adverse events are classified as serious or non-serious. A serious adverse event is any AE that, in the view of either the investigator or the sponsor, is:

- fatal
- life-threatening
- requires or prolongs hospital stay
- results in persistent or significant disability or incapacity
- a congenital anomaly or birth defect
- an important medical event when the event does not fit the other outcomes, but the event may jeopardize the patient and may require medical or surgical intervention (treatment) to prevent one of the other outcomes.
- required intervention to prevent permanent impairment or damage (for devices only)

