10.11 Stopping Rules (Criteria for Pausing Trial)

Refer to Study Design and Endpoints, for a description of “3+3” design and enrollment sequence of each cohort.

The stopping rules for this study are any of the following:

- If at any time during the study two thirds of participants in a single cohort experience a DLT after product administration
- If 2 or more participants across all enrolled cohorts experience the same grade ≥ 3 adverse event or grade ≥ 3 adverse event in the same organ class
- In the event of any unexpected Grade 4 toxicities
- Any SAE, potentially life-threatening AE or death
- Any reported anaphylaxis from dMAb AZD5396 and dMAb AZD8076 and Hylenex® delivered by EP.

The study will be halted for any report of anaphylaxis from dMAb AZD5396 and dMAb AZD8076 and Hylenex® delivered by EP. The study will be halted to enrollment and further dosing will be suspended until a full discussion has been conducted and then reviewed by the DSMB and study resumption is agreed upon.

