10.13 Adverse Event Reporting

10.13.1 Reporting Period

Adverse events will be reported from the time of informed consent until the subject completes the study.

Every SAE, regardless of suspected causality (e.g., relationship to study product(s) or study procedure(s) or disease progression) must be reported to the sponsor within 24 hours of learning of its occurrence.

Recurrent episodes, complications, or progression of the initial SAE must be reported to the Sponsor as a follow-up to the original episode within 24 hours of the investigator receiving the follow-up information. A SAE considered completely unrelated to a previously reported one should be reported separately as a new event. Send the SAE report to the sponsor.

New information regarding the SAE will be reported as it becomes available and in the same manner that the initial SAE (i.e., SAE form). The investigator must follow the event to resolution or until the event is deemed and documented irreversible, whichever is longer.

The investigator will report AEs and SAEs to the IRB/EC of record and other local regulatory groups per the local requirements.

The study sponsor will be responsible for notifying the Health Authority(ies), Food and Drug Administration (FDA), as applicable of any unexpected fatal or life-threatening suspected adverse reaction per applicable regulations. In addition, the sponsor must notify Health Authority(ies), FDA, as applicable and all participating investigators of potential serious risks, from clinical trials or any other source, as per the applicable regulation.

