Tenderness	Mild discomfort to touch	Discomfort with movement	Significant discomfort at rest	ER visit or hospitalization
Erythema/Redness *	2.5 – 5 cm	5.1 – 10 cm	> 10 cm	Necrosis or exfoliative dermatitis
Induration/Swelling **	2.5 – 5 cm and does not interfere with activity	5.1 – 10 cm or interferes with activity	> 10 cm or prevents daily activity	Necrosis

* In addition to grading the measured local reaction at the greatest single diameter, the measurement should be recorded as a continuous variable.

** Induration/Swelling should be evaluated and graded using the functional scale as well as the actual measurement.

Contains Nonbinding Recommendations

Vital Signs *	Mild (Grade 1)	Moderate(Grade 2)	Severe (Grade 3)	Potentially Life Threatening (Grade 4)
Fever (°C) ** (°F) **	38.0 – 38.4 100.4 – 101.1	38.5 – 38.9 101.2 – 102.0	39.0 – 40 102.1 – 104	> 40 ≥ 104
Tachycardia - beats per minute	101 – 115	116 – 130	> 130	ER visit or hospitalization for arrhythmia
Bradycardia - beats per minute***	50 – 54	45 – 49	< 45	ER visit or hospitalization for arrhythmia
Hypertension (systolic) - mm Hg	141 – 150	151 – 155	> 155	ER visit or hospitalization for malignant hypertension
Hypertension (diastolic) - mm Hg	91 – 95	96 – 100	> 100	ER visit or hospitalization for malignant hypertension
Hypotension (systolic) - mm Hg	85 – 89	80 – 84	< 80	ER visit or hospitalization for hypotensive shock
Respiratory Rate – breaths per minute	17 – 20	21 – 25	> 25	Intubation

* Subject should be at rest for all vital sign measurements.

** Oral temperature; no recent hot or cold beverages or smoking.

*** When resting heart rate is between 60 – 100 beats per minute. Use clinical judgement when characterizing bradycardia among some healthy subject populations, for example, conditioned athletes.

Systemic (General)	Mild (Grade 1)	Moderate(Grade 2)	Severe (Grade 3)	Potentially Life Threatening (Grade 4)
Nausea/vomiting	No interference with activity or 1 – 2 episodes/24 hours	Some interference with activity or > 2 episodes/24 hours	Prevents daily activity, requires outpatient IV hydration	ER visit or hospitalization for hypotensive shock
Diarrhea	2 – 3 loose stools or ≤ 400 gms/24 hours	4 – 5 stools or 400 – 800 gms/24 hours	6 or more watery stools or > 800gms/24 hours or requires outpatient IV hydration	ER visit or hospitalization

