Headache	No interference with activity	Repeated use of non-narcotic pain reliever > 24 hours or some interference with activity	Significant; any use of narcotic pain reliever or prevents daily activity	ER visit or hospitalization
Fatigue	No interference with activity	Some interference with activity	Significant; prevents daily activity	ER visit or hospitalization
Myalgia	No interference with activity	Some interference with activity	Significant, prevents daily activity	ER visit or hospitalization

Contains Nonbinding Recommendations

Systemic Illness	Mild (Grade 1)	(Moderate(Grade 2)	Severe (Grade 3)	Potentially Life Threatening (Grade 4)
Illness or clinical adverse event (as defined according to applicable regulations)	No interference with activity	Some interference with activity not requiring medical intervention	Prevents daily activity and requires medical intervention	ER visit or hospitalization

Contains Nonbinding Recommendations
B. Tables for Laboratory Abnormalities

The laboratory values provided in the tables below serve as guidelines and are dependent upon institutional normal parameters. Institutional normal reference ranges should be provided to demonstrate that they are appropriate.

Serum *	Mild (Grade 1)	Moderate (Grade 2)	Severe (Grade 3)	Potentially Life Threatening (Grade 4)**
Sodium - Hyponatremia mEq/L	132 - 134	130 - 131	125 - 129	< 125
Sodium - Hypernatremia mEq/L	144 - 145	146 - 147	148 - 150	> 150
Potassium - Hyperkalemia mEq/L	5.1 - 5.2	5.3 - 5.4	5.5 - 5.6	> 5.6
Potassium - Hypokalemia mEq/L	3.5 - 3.6	3.3 - 3.4	3.1 - 3.2	< 3.1
Glucose - Hypoglycemia mg/dL	65 - 69	55 - 64	45 - 54	< 45
Glucose - Hyperglycemia				Insulin requirements or hyperosmolar coma
Fasting - mg/dL	100 - 110	111 - 125	> 125	
Random - mg/dL	110 - 125	126 - 200	> 200	
Blood Urea Nitrogen BUN mg/dL	23 - 26	27 - 31	> 31	Requires dialysis
Creatinine - mg/dL	1.5 - 1.7	1.8 - 2.0	2.1 - 2.5	> 2.5 or requires dialysis
Calcium - hypocalcemia mg/dL	8.0 - 8.4	7.5 - 7.9	7.0 - 7.4	< 7.0
Calcium - hypercalcemia mg/dL	10.5 - 11.0	11.1 - 11.5	11.6 - 12.0	> 12.0
Magnesium - hypomagnesemia mg/dL	1.3 - 1.5	1.1 - 1.2	0.9 - 1.0	< 0.9
Phosphorous - hypophosphatemia mg/dL	2.3 - 2.5	2.0 - 2.2	1.6 - 1.9	< 1.6
CPK - mg/dL	1.25 - 1.5 x ULN***	1.6 - 3.0 x ULN	3.1 - 10 x ULN	> 10 x ULN
Albumin - Hypoalbuminemia g/dL	2.8 - 3.1	2.5 - 2.7	< 2.5	--
Total Protein - Hypoproteinemia g/dL	5.5 - 6.0	5.0 - 5.4	< 5.0	--

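### Section 7.3 exempts a hospital stay for unresolved post-dose vital signs from being an SAE, but Section 10.1.2 has no such exception, so the 24-hour report and the pause for any SAE depend on which section is followed

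*Protocol*

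**What the plan says.** Protocol Section 7.3 applies to each dosing visit. Participants go home once vital signs are normal or back to their pre-injection baseline. If they have not recovered within 4 hours, the participant stays in hospital under continuous monitoring. On the status of that stay, 7.3 says: "This hospitalization will not be considered a SAE but a protocol procedure unless the event progresses and places the subject at risk".

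Section 10.1.2 defines an SAE as any AE that, "in the view of either the investigator or the sponsor", meets one of a list of criteria. One is that the event "requires or prolongs hospital stay". The list has no exception for observation stays or protocol procedures and does not refer to 7.3.

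Two safeguards depend on the SAE label:

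- Section 10.13.1: every SAE, whatever its suspected cause, "must be reported to the sponsor within 24 hours of learning of its occurrence". Section 10.3 repeats the 24-hour rule, including for events related to the procedure.
- Section 10.11: the criteria for pausing the trial include "Any SAE, potentially life-threatening AE or death".

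SAE occurrence is also a primary safety endpoint (Section 3.2).

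**The concern.** The stay in 7.3 is not a scheduled admission. An abnormal finding after dosing sets it off. Where that finding is an AE, 10.1.2 read on its own makes it serious because of the stay. Section 7.3 says the stay does not, unless the event both worsens and endangers the participant. That two-part test appears nowhere in 10.1.2. An event that is severe from the start and simply persists can fail the 7.3 test and still meet the hospital-stay criterion.

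At stake is whether the sponsor is told within 24 hours and whether dosing pauses. In a dose-escalation trial in healthy volunteers, with cohorts of 3 to 6, one unplanned hospital stay is information that the next dosing decision should have. It should not turn on whether staff work from the visit procedures or from the safety chapter.

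**Working it through.** The plan states no figure on this point. The check sets the sections side by side.

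**Step 1: which readings can lead to a stay, and how they are graded.** Section 7.3 gives the normal ranges and Appendix B the grades. I assume that a participant kept in hospital has a reading both off baseline and outside the normal range, because 7.3 allows discharge on either.

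| Vital sign | Outside 7.3 range | Ungraded | Grade 1 | Grade 2 | Grade 3 |
|---|---|---|---|---|---|
| Systolic, high (mmHg) | ≥140 | 140 | 141-150 | 151-155 | >155 |
| Systolic, low (mmHg) | ≤90 | 90 | 85-89 | 80-84 | <80 |
| Diastolic, high (mmHg) | ≥100 | none | none | 100 | >100 |
| Pulse, high (per min) | >100 | none | 101-115 | 116-130 | >130 |
| Pulse, low (per min) | <60 | 55-59 | 50-54 | 45-49 | <45 |
| Respiratory rate, high (per min) | ≥20 | none | 20 | 21-25 | >25 |
| Temperature (°C) | febrile | none | 38.0-38.4 | 38.5-38.9 | 39.0-40 |

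Stays can therefore arise at every grade from ungraded to Grade 3. In the row "Hypertension (diastolic) - mm Hg", a stay for a raised value is Grade 2 at exactly 100 and Grade 3 at anything above.

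**Step 2: one case under each section.** Take a diastolic of 105 mmHg after dosing (Grade 3), still raised at 4 hours, kept overnight and not progressing.

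| | Following 7.3 | Following 10.1.2 |
|---|---|---|
| Does the stay make the event an SAE? | No | Yes |
| 24-hour SAE report (10.13.1) | Not triggered | Triggered |
| Any-SAE pause (10.11) | Not triggered | Triggered |

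A systolic of 145 mmHg (Grade 1) kept in hospital splits in the same way, because neither section has a grade limit.

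**Step 3: would another pause criterion in 10.11 catch the single Grade 3 event?**

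- *Two thirds of a cohort with a DLT.* On planned cohort sizes this needs 2 of 3 (2/3 × 3 = 2), 4 of 5 (2/3 × 5 = 3.33, rounded up) or 4 of 6 (2/3 × 6 = 4). One event does not meet it. If only participants dosed so far are counted, a sentinel's DLT would, but the event must first be a DLT.
- *The same Grade 3 or higher event, or one in the same organ class, in two or more participants.* One event does not meet it.
- *Unexpected Grade 4, potentially life-threatening AE, death or anaphylaxis.* A stable Grade 3 vital sign is none of these.

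That leaves the SAE label as the deciding criterion.

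**Step 4: would the DLT rules catch it?** Section 10.10 counts Grade 3 or greater systemic symptoms that the Principal Investigator judges related. Hypotension and fever are among the systemic reactions named in Sections 9.4.1 and 9.8.2, so they plausibly qualify when related. Hypertension and tachycardia are not named there. An event judged unrelated is not a DLT at all. When the event is a DLT, it brings an expedited report to the FDA (10.13.2), withholding of that participant's second dose (7.3) and, among a cohort's first three participants, an ad hoc DSMB review (4.2).

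**The case against.** The strongest reply is that 7.3 is a deliberate, specific rule for one named stay, and that a specific rule governs a general definition. On that view the 4-hour rule required the stay, not the AE. Section 10.1.2 also leaves seriousness to the investigator or sponsor, so it is too strong to say that one such stay necessarily pauses the trial. The study is single-centre and open-label, and the protocol refers to a sponsor-investigator, so divergent readings are less likely than in a multicentre trial. The event is not lost either: it is recorded as an AE with its severity (10.8), the DSMB reviews all safety data (14.2.1), and the important-medical-event criterion remains available.

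Much of this stands. The exemption is sensible for mild findings, and 7.3 may well have been meant to prevail. But Sections 10.1.2, 10.11 and 10.13.1 do not say so, and staff working from them would see no exception. The judgement clause helps little if the site, following 7.3, sends no report: the sponsor then gets no prompt occasion to form its own view. If 7.3 does prevail, a stable Grade 3 event with a hospital stay skips both safeguards, so a bare cross-reference would leave the gap in place.

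A reader might infer a second ambiguity from Appendix B. Its row "Illness or clinical adverse event (as defined according to applicable regulations") makes any hospitalization Grade 4, which could seem to turn every stay into a Grade 4 event and so meet "In the event of any unexpected Grade 4 toxicities" if unexpected. The documents do not support that well. Vital signs have their own rows, which for blood pressure and pulse reserve Grade 4 for malignant hypertension, hypotensive shock or arrhythmia. The general row reads naturally as a catch-all for events without one. If it did apply, the trial would pause for a potentially life-threatening AE whatever the SAE status, which would narrow the gap.

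**Conclusion.** The conflict is real. It covers every 7.3 stay that accompanies a vital-sign AE, at any grade. Its practical weight lies in a single, non-progressing Grade 3 event, mainly hypertension or tachycardia, or any Grade 3 vital-sign event judged unrelated. For these the DLT and two-matching-event rules are only a partial backstop, and whether the stay triggers the 24-hour report and the pause is undetermined.

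Two stronger readings do not hold. One is that the conflict is confined to Grade 3 stays: 10.1.2 has no grade limit, and the Grade 3 emphasis reflects consequence, not scope. The other is that such stays are likely because the 7.3 diastolic limit sits next to the Grade 3 boundary. That closeness gives the grade of a reading, not its chance. The protocol gives no frequency, Table 1 lists no blood-pressure event among the expected risks, and Section 5.2 excludes people with repeated readings above 140/95.

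No analysis or estimate is shown to be wrong. The conclusion rests on reading the sections as written and on the discharge assumption in the working.

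**What to change.** - **7.3:** limit the exemption to precautionary observation with no AE, or with a Grade 1-2 vital-sign finding that needs no treatment. Assess every other stay (Grade 3 or higher, or needing medical intervention) under 10.1.2 without the exemption, so that the hospital-stay criterion applies. Grade then decides only whether the exemption is available. Seriousness is still judged under 10.1.2, in keeping with 10.8, which lists severity and seriousness as separate attributes.
- **10.1.2 and 10.11:** state the same exception in both.
- **Notification:** tell the sponsor within 24 hours, and the DSMB promptly, of every 7.3 stay, exempt or not.

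The cost is wording in three sections, a few extra notifications, and an occasional pause for an event that proves benign. A persistent systolic of 141-150 mmHg or a temperature of 38.0-38.4 °C that needs no treatment stays exempt, so a mild finding of this kind would not pause the trial.

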7.4 Day 7 (Week 1)

The following evaluations will be performed at this visit:

- Conduct targeted injection site reaction systemic and local assessment.
- Collect all present and/or new or ongoing adverse events.
- Document any present conditions and concomitant illnesses (including history of new COVID 19 diagnosis).
- Record current concomitant medications/treatments.
- Targeted physical examination.
- Record vital signs including heart rate (HR), respiratory rate (RR), blood pressure (BP), oral temperature.
- Collect blood for PT(INR) and aPTT, CBC with differential, serum chemistry, CPK.
- Collect urine for urinalysis.
- Collect serum for mAb AZD5396 and mAb AZD8076 level assessment and ADA evaluation.
- Perform 12 lead ECG.

7.5 Day 10 (cohorts B-G only)

The following evaluations will be performed at this visit:

- Conduct targeted injection site reaction systemic and local assessment.
- Collect all present and/or new or ongoing adverse events.
- Document any present conditions and concomitant illnesses (including history of new COVID 19 diagnosis).
- Record current concomitant medications/treatments.
- Targeted physical examination.
- Record vital signs including heart rate (HR), respiratory rate (RR), blood pressure (BP), oral temperature.
- Collect blood for PT(INR) and aPTT, CBC with differential, serum chemistry, CPK.
- Collect urine for urinalysis.

- Collect serum for mAb AZD5396 and mAb AZD8076 level assessment and ADA evaluation.
- Perform 12 lead ECG.

7.6 Week 2, Week 3, Week 4, Week 5, Week 6, Week 8, Week 12, Week 16, Week 24, and Week 52

The following evaluations will be performed at these visits:

- Conduct targeted injection site reaction systemic and local assessment (cohort G, Week 5 and 6).
- Collect all present and/or new or ongoing adverse events.
- Document any present conditions and concomitant illnesses (including history of new COVID 19 diagnosis).
- Record current concomitant medications/treatments.
- Targeted physical examination.
- Record vital signs including heart rate (HR), respiratory rate (RR), blood pressure (BP), oral temperature.
- Collect blood for PT(INR) and aPTT, CBC with differential, serum chemistry, CPK
- Collect urine for urinalysis.
- Collect serum for mAb AZD5396 and mAb AZD8076 level assessment and ADA evaluation.
- Perform 12-lead ECG

7.7 Week 32, Week 42, and additional PK/ADA measurements

The following evaluations will be performed at weeks 32 and 42:

- Collect all present and/or new or ongoing adverse events.
- Collect serum for mAb AZD5396 and mAb AZD8076 level assessment and ADA evaluation.

Participants may be asked to come in for additional PK/ADA monitoring between weeks 52 and 72, at the investigators' discretion.

Participants may be asked to come in for additional PK/ADA monitoring between weeks 72 and 98, at the investigators' discretion.

7.8 Week 72 / Early Termination Visit

The following evaluations will be performed at the visit:

- Collect all present and/or new or ongoing adverse events
- Document any present conditions and concomitant illnesses (including history of new COVID 19 diagnosis)
- Record current concomitant medications/treatments
- Full physical examination

- Record vital signs including body weight and height, heart rate (HR), respiratory rate (RR), blood pressure (BP), oral temperature
- Collect blood for PT(INR) and aPTT, CBC with differential, serum chemistry, and CPK
- Collect urine for urinalysis
- Collect serum for mAb AZD5396 and mAb AZD8076 level assessment and ADA evaluation
- Perform 12 lead ECG

8 STUDY INTERVENTION DISCONTINUATION AND PARTICIPANT DISCONTINUATION/WITHDRAWAL

8.1 Discontinuation of Study Intervention

Discontinuation from study intervention does not mean discontinuation from the study, and remaining study procedures should be completed as indicated by the study protocol. If a clinically significant finding is identified (including, but not limited to changes from baseline) after enrollment, the investigator or qualified designee will determine if any change in participant management is needed. Any new clinically relevant finding will be reported as an adverse event (AE).

The data to be collected at the time of study intervention discontinuation will include the following:

- Clinical laboratory evaluations (CBC, CMP, and any other necessary at the discretion of the PI).
- PK evaluation

8.2 Participant Discontinuation/Withdrawal from the Study

Participants are free to withdraw from participation in the study at any time upon request. An investigator may discontinue or withdraw a participant from the study for the following reasons:

- Pregnancy
- If any clinical adverse event (AE), laboratory abnormality, or other medical condition or situation occurs such that continued participation in the study would not be in the best interest of the participant
- Disease progression which requires discontinuation of the study intervention
- If the participant meets an exclusion criterion (either newly developed or not previously recognized) that precludes further study participation

The reason for participant discontinuation or withdrawal from the study will be recorded on the Case Report Form (CRF). Subjects who sign the informed consent form and are scheduled for Day 0 but do not receive the study drug may be replaced. Subjects who sign the informed consent form and receive the study intervention, and subsequently withdraw, or are withdrawn or discontinued from the study, will be replaced at the discretion of the Investigator. Subjects in cohorts B, C, D, E, and F may be replaced if they do not receive both the Day 0 and the Day 3 doses. Subjects in cohort G may be replaced if they do not receive all four of the Day 0, 3, 28, and 31 doses. Subjects in these cohorts who

only receive Day 0 doses and want to continue in the study will be included in the A1 or A2 group for analysis.

